8.4 UNANTICIPATED PROBLEMS

8.4.1 DEFINITION OF UNANTICIPATED PROBLEMS (UP)

The Office for Human Research Protections (OHRP) considers unanticipated problems involving risks to participants or others to include, in general, any incident, experience, or outcome that meets **all** of the following criteria:

- Unexpected in terms of nature, severity, or frequency given (a) the research procedures that are described in the protocol-related documents, such as the Institutional Review Board (IRB)-approved research protocol and informed consent document; and (b) the characteristics of the participant population being studied;
- Related or possibly related to participation in the research (“possibly related” means there is a reasonable possibility that the incident, experience, or outcome may have been caused by the procedures involved in the research); and
- Suggests that the research places participants or others at a greater risk of harm (including physical, psychological, economic, or social harm) than was previously known or recognized.

8.4.2 UNANTICIPATED PROBLEM REPORTING

An investigator shall submit to the sponsor and to the reviewing Institutional Review Board (IRB) a report of any unanticipated adverse device effect occurring during an investigation as soon as possible, but in no event later than 10 working days after the investigator first learns of the effect (21 CFR 812.150(a)(1)). A sponsor who conducts an evaluation of an unanticipated adverse device effect under 812.46(b) shall report the results of such evaluation to the Food and Drug Administration (FDA) and to all reviewing IRB's and participating investigators within 10 working days after the sponsor first receives

The Caffeine, Postoperative Delirium, And CHange IN Outcomes after Surgery-2 (CAPACHINOS-2) Study Protocol <2.0>

Version <2.0>
<14 December 2022>

notice of the effect. Thereafter the sponsor shall submit such additional reports concerning the effect as FDA requests (21 CFR 812.150(b)(1)).

8.4.3 REPORTING UNANTICIPATED PROBLEMS TO PARTICIPANTS

Participants will be informed of UPs in accordance with IRB and sponsor recommendations.

9 STATISTICAL CONSIDERATIONS

9.1 STATISTICAL HYPOTHESES

- Primary Efficacy Endpoint(s):

This trial tests the primary hypothesis that intravenous caffeine citrate, administered during surgical closure, and on the first two postoperative mornings, will reduce the incidence of postoperative delirium as identified by the long-form CAM screening tool.¹ The CAM will be complemented by a validated chart review method^{65,66} to account for any episodes of delirium for a given day not detected by the in-person CAM assessment.

9.2 SAMPLE SIZE DETERMINATION

Both caffeine groups will be compared to the placebo group based on Generalized Estimating Equation (GEE) modeling. Sample size calculations were thus conducted via GEE Tests for Multiple Proportions in a Cluster-Randomized Design with Power Analysis and Sample Size Software (2022; NCSS, LLC. Kaysville, Utah, USA).⁹⁰ Significance level (α) was set at 0.05. A baseline early postoperative delirium incidence (including the PACU timeframe) of 30% was conservatively estimated based on our preliminary trial.²⁰ A sample size of 250 participants will provide between 80-95% power assuming a baseline delirium incidence of 30%, an incidence ranging between 10-30% in the low-dose group, and an incidence between 10-15% in the high-dose group. These effect sizes are estimated from our preliminary trial data with a similar dosing range (1.7 – 4.5 mg/kg; median dose 2.5 mg/kg) and absolute risk reduction >20%.²⁰ Increased potency may be expected with older patients given the reduced pharmacologic volume of distribution⁷⁴ and a possible age-caffeine interaction effect with respect to cognition.⁷³ This sample size also accounts for an approximate 10% dropout rate. Lastly, no interim analyses are planned in relation to the primary outcome.

9.3 POPULATIONS FOR ANALYSES

The primary analysis for this study will follow an intention-to-treat approach. That is, patients will be analyzed based on initial group allocation, regardless of protocol deviations (e.g., not receiving the study drug). A secondary, per-protocol approach will then be performed, which will include all randomized participants who received the study drug as intended and with available delirium assessments for each corresponding day.

9.4 STATISTICAL ANALYSES

9.4.1 GENERAL APPROACH

For descriptive statistics, categorical outcomes will be presented as proportions (frequencies) and continuous data will be presented as means (\pm standard deviation) or medians (interquartile range). Normality of distribution will be assessed using the Shapiro-Wilk test, and parametric or non-parametric tests will be applied as appropriate. For statistical modeling, covariates will be specified in the following

The Caffeine, Postoperative Delirium, And CHange IN Outcomes after Surgery-2 (CAPACHINOS-2) Study Protocol <2.0>

Version <2.0>
<14 December 2022>

sections. All inferential testing will be two-sided, and p-values <0.05 will be considered statistically significant. 95% confidence intervals will be reported.

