4 STUDY DESIGN

4.1 OVERALL DESIGN

The **central hypothesis** of this study is that intravenous caffeine will reduce the incidence of postoperative delirium. This will be a Phase II, single-center, quadruple-blinded, placebo-controlled, block-randomized trial. Written informed consent will be obtained from all participants, and institutional review board approval will be obtained. The trial will follow a parallel design, and participants will be block-randomized with a 1:1:1 allocation ratio (placebo: 1.5 mg/kg caffeine: 3 mg/kg caffeine).

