9.4.2 ANALYSIS OF THE PRIMARY EFFICACY ENDPOINT(S)

As previously described, postoperative delirium will serve as the primary endpoint. The primary analytical test will be a multivariable logistic regression model that will follow the GEE approach. Independent variables will include the placebo group (reference), low-dose caffeine group, high-dose caffeine group, and *a priori* variables that may be independently predictive of delirium (e.g., age, male sex, American Society of Anesthesiologists Physical Status score, baseline cognitive function via Montreal Cognitive Assessment, baseline functional status via Instrumental Activities of Daily Living, depression, and epidural use⁸³). Baseline cohort imbalances, defined by absolute standardized differences >0.20, will also be included in this model.

Lastly, missing delirium data will be assessed for randomness using the Little's Missing Completely at Random Test. If data are missing at random, imputation will be performed, and these results will be compared to results with the actual data in the supplementary appendix. If data are not missing at random, no imputation will be performed, and the Cochran-Armitage test will be used to assess for the proportion of missing data across each arm.

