9.4.3 ANALYSIS OF THE SECONDARY ENDPOINT(S)

For secondary endpoints, a similar GEE-based approach will be used. Within- and between- group comparisons will be analyzed based on coefficients in the model. This approach also allows for flexibility with missing data. Unstandardized beta coefficients will be presented with 95% confidence intervals and p-values (<0.05 will be considered statistically significant).

For non-repeated continuous measures (e.g., delirium duration, cumulative opioid consumption) and binary outcomes (e.g., postoperative delirium, headache), we will use the same GEE modeling approach. All GEE models will use the empirical parameter estimates with an exchangeable correlation matrix. As indicated previously, models will adjust for baseline cohort imbalances. Additionally, for Quality of Recovery and headache severity, the differential effect of habitual caffeine consumption and group will be tested. This will be tested via interaction term of habitual caffeine consumption with caffeine group (placebo, low-dose caffeine group, high-dose). The daily number of caffeinated beverages will be recorded for each participant, and the resulting distribution will be analyzed and used to inform the most appropriate categorization of habitual caffeine users (e.g., non-users, low-dose, high-dose, etc.).

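### Two caffeine doses are each tested against placebo at p<0.05 for one primary hypothesis, with no rule for how the two results decide it; if either dose alone counts as success, familywise error is about 9% two-sided instead of 5%

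*Protocol*

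**What the plan says.** Protocol 9.1 states one primary hypothesis, for caffeine as a whole: that it "will reduce the incidence of postoperative delirium as identified by the long-form CAM screening tool".

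Three passages of section 9 bear on how it is tested:

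- **9.2** says that "Both caffeine groups will be compared to the placebo group based on Generalized Estimating Equation (GEE) modeling" and that "Significance level (α) was set at 0.05". The sample size comes from a GEE test for multiple proportions, that is, a k-group test with one alpha.
- **9.4.2** names a multivariable logistic GEE model as the primary analysis: "Independent variables will include the placebo group (reference), low-dose caffeine group, high-dose caffeine group, and" prespecified predictors. Each dose therefore has its own coefficient against placebo.
- **9.4.1** sets the general rule: "All inferential testing will be two-sided, and p-values <0.05 will be considered statistically significant".

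Allocation is 1:1:1 (4.1). No interim efficacy analysis is planned (9.2, 9.4.6), so alpha is not spent elsewhere on the primary outcome.

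**The concern.** There are two routes to one claim. Read literally, 9.4.1 lets the low-dose coefficient or the high-dose coefficient, each at p<0.05, be called significant, and either could then be presented as confirming that caffeine reduces delirium. Under that reading the design does not hold the 5% level set in 9.2.

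The planning assumptions make this reading natural. Section 9.2 claims 80-95% power over a low-dose incidence of up to 30%, which equals the placebo rate. A rule that both doses must succeed could not have that power when the low dose does nothing.

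The sizing test and the analysis also fail to connect. The k-group test in 9.2 would protect the 5% level if it were the primary test or a gate, but 9.4.2 gives it neither role. The error rate of the primary claim thus depends on a choice that the protocol leaves open and that could be made after the results are known.

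**Working it through.** **Inputs.** Two contrasts with a shared placebo arm (9.2, 9.4.2); two-sided 0.05 for each (9.4.1); 1:1:1 allocation (4.1); N=250, about 10% dropout, placebo 30%, low dose 10-30%, high dose 10-15% (9.2). Evaluable per arm: 250 × 0.9 / 3 = 75; with no dropout, 250 / 3 ≈ 83.

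**The plan's own figure (power 80-95%).** For a 3-group test on 2 df, the noncentrality is λ = n Σ(pᵢ − p̄)² / [p̄(1 − p̄)].

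- Rates 30/10/10 (placebo/low/high, %), n=75: p̄ = 0.1667, λ = 75 × 0.02667 / 0.1389 = 14.4, power 93.5%.
- Rates 30/30/10: p̄ = 0.2333, λ = 75 × 0.02667 / 0.1789 = 11.2, power 85.9%.

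Over all low-dose rates the power is 78-93% when the high-dose rate is 10%, close to the stated range, but only 49-85% when it is 15%. The protocol gives neither cluster size nor within-patient correlation, so an exact check is impossible. That is a separate matter and does not affect the error rate below.

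**Familywise error, both true effects zero.** The two differences share the placebo mean, so their correlation is (σ²/n) / (2σ²/n) = 0.5.

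- Either direction: 1 − P(|Z₁| ≤ 1.96 and |Z₂| ≤ 1.96) = 0.0907.
- Benefit direction only: 1 − P(Z₁ > −1.96 and Z₂ > −1.96) = 0.0454, against 0.025 for one two-sided test.
- Inflation: 0.0907 / 0.05 ≈ 1.8 and 0.0454 / 0.025 ≈ 1.8.

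A simulation with one binary outcome per patient, 75 and 83 per arm, common event rates of 20% and 30%, and 400,000 trials per setting gives:

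| Rule | At least one false finding |
|---|---|
| Either dose at 0.05, either direction | 8.8-9.3% |
| Either dose at 0.05, benefit only | 4.4-4.7% |
| 2-df test at 0.05 first, then each dose at 0.05 | 4.1-4.2% |
| Holm on the two contrasts | 4.5-4.8% |

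**Power for the high dose, 75 per arm (same simulation, unadjusted pairwise tests of proportions).**

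| Rates, placebo/low/high (%) | Each at 0.05 | With gate | With Holm |
|---|---|---|---|
| 30/30/10 | 88.5% | 85.0% | 81.6% |
| 30/20/10 | 88.5% | 79.9% | 81.8% |
| 30/15/10 | 88.5% | 82.2% | 83.0% |
| 30/10/10 | 88.6% | 86.6% | 86.0% |
| 30/30/15 | 60.2% | 51.3% | 49.1% |
| 30/20/15 | 60.2% | 48.4% | 50.7% |
| 30/15/15 | 60.0% | 53.9% | 53.8% |
| 30/10/15 | 60.1% | 58.9% | 58.1% |

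The gate costs 1 to 9 points in seven of the eight settings and 12 at 30/20/15. Holm costs 2 to 11.

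**Fixed sequence, high dose then low dose, at 30/10/15.** The high-dose test loses nothing, but low-dose power falls from 88.6% to 57.3%, and the chance of any positive result from 91.4% to 60.1%.

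**The case against.** - **The hypothesis is directional.** A reader might infer a 9% chance of falsely claiming that caffeine reduces delirium. The documents do not support that: a significant increase would not confirm the hypothesis in 9.1, and the 9% counts such results. The figure for a false benefit claim is about 4.5% against 2.5%. The inflation factor is the same.
- **The protocol does not say that either dose suffices.** This is correct. 9.4.2 does not state whether the decision rests on single coefficients or on the joint group effect. A reader might conclude that the analysis omits the global test altogether, but the text only fails to say which test is drawn from the model. If the k-group test of 9.2 is meant as the gate, the error is about 4%. The gap is then one of statement, and it still has to be closed.
- **The SAP may deal with it.** It may, so nothing here shows that the trial as a whole lacks multiplicity control. But the protocol is not silent: it fixes p<0.05 for every test. A SAP with an order or an adjustment would have to qualify that sentence.
- **This is Phase 2.** Phase 2 trials often tolerate more error, but this one names a primary hypothesis, an alpha and a power claim, and 10.1.6 requires adequate power for the primary analysis.

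A reader might also extend the point to the secondary endpoints, since 9.4.3 repeats the 0.05 threshold. A large combined error there would need roughly independent endpoints. Severity and duration come from the same CAM assessments, and sedation and agitation from the same RASS readings; no confirmatory claim is attached to any of them. That extension is not made here.

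**Conclusion.** The point holds for the primary endpoint. As written, 9.2, 9.4.1 and 9.4.2 test two doses against a shared placebo arm at two-sided 0.05 each and give no rule for combining the results. Depending on the unstated rule, the two-sided familywise error lies between about 4% (2-df gate) and about 9% (either dose suffices). For a false claim of benefit, the either-dose reading gives about 4.5% instead of 2.5%.

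These figures assume equal arms, no true effect of either dose, and a correlation of 0.5 between the contrasts. Covariate adjustment and the repeated-measures structure could shift them slightly. The rule should be settled before unblinding; it is not a fatal fault in the design.

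**What to change.** Amend 9.4.2 to state the decision rule, in one of two forms:

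1. **Global gate.** The 2-df joint test of the two dose coefficients in the primary GEE model must be significant at two-sided 0.05 before either dose-versus-placebo contrast, tested at two-sided 0.05, is declared significant. With three groups this is a closed procedure and controls the familywise error strongly. It also matches the test used for sizing.
2. **Holm.** The smaller of the two p-values is compared with 0.025 and, if significant, the larger with 0.05.

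In either case, state that a benefit claim needs an effect in the favourable direction, and exempt these contrasts from the general 0.05 rule in 9.4.1.

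The cost is a few sentences and the power losses tabulated above, for example 88.5% to 85.0% with the gate at 30/30/10 and 60.2% to 51.3% at 30/30/15. N need not change for the larger effect: 30% versus 10% at alpha 0.025 with 80% power takes 75 per arm, 3 × 75 = 225, and 225 / 0.9 = 250. At 30% versus 15%, pairwise power is only about 60% even without adjustment.

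A fixed high-then-low sequence also controls the error, but it suits only a sponsor who accepts the loss shown at 30/10/15. Section 9.2 allows those rates, and 4.3 itself argues that the lower dose may suit this older population.

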9.4.2 ANALYSIS OF THE PRIMARY EFFICACY ENDPOINT(S)

As previously described, postoperative delirium will serve as the primary endpoint. The primary analytical test will be a multivariable logistic regression model that will follow the GEE approach. Independent variables will include the placebo group (reference), low-dose caffeine group, high-dose caffeine group, and *a priori* variables that may be independently predictive of delirium (e.g., age, male sex, American Society of Anesthesiologists Physical Status score, baseline cognitive function via Montreal Cognitive Assessment, baseline functional status via Instrumental Activities of Daily Living, depression, and epidural use⁸³). Baseline cohort imbalances, defined by absolute standardized differences >0.20, will also be included in this model.

Lastly, missing delirium data will be assessed for randomness using the Little's Missing Completely at Random Test. If data are missing at random, imputation will be performed, and these results will be compared to results with the actual data in the supplementary appendix. If data are not missing at random, no imputation will be performed, and the Cochran-Armitage test will be used to assess for the proportion of missing data across each arm.

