1 PROTOCOL SUMMARY

1.1 SYNOPSIS

Title:	The CAffeine, Postoperative delirium, And CHange IN Outcomes after Surgery-2 (CAPACHINOS-2) Study
Study Description:	The objective of this study is to test the effects of caffeine on neurocognitive and clinical recovery after major surgery. Specifically, this trial tests the primary hypothesis that caffeine will reduce the incidence of postoperative delirium.
Objectives:	
Primary objective: The primary objective is to determine whether postoperative caffeine reduces the incidence of postoperative delirium, based on standardized delirium assessment methodology.
 
Secondary Objectives: To determine (1) whether caffeine improves postoperative patient satisfaction, based on validated, patient-reported quality of recovery measures, and (2) neural correlates of delirium and Mild Cognitive Impairment, based on advanced electroencephalographic (EEG) analysis.

Endpoints:	
Primary Endpoint: Incidence (%) of postoperative delirium, measured via long-form Confusion Assessment Method (CAM).¹
 
Secondary Endpoints:
 
-- Delirium severity (CAM-S)²-- Delirium duration (days, n)-- Patient-reported 15-item Quality of Recovery score³-- Agitation (via Richmond Agitation and Sedation Scale, RASS)⁴-- Sedation (via Richmond Agitation and Sedation Scale, RASS)⁴-- Headache severity (10-centimeter visual analog scale, VAS)-- Cumulative opioid consumption (oral morphine equivalents, mg)

The CAffeine, Postoperative Delirium, And CHange IN Outcomes after Surgery-2 (CAPACHINOS-2) Study Protocol <2.0>

[figure not shown]
Version <2.0>
<14 December 2022>

Study Population:	In total, surgical patients (n=250; ≥70 years of age) presenting for major non-cardiac, non-intracranial neurologic surgery will be recruited at Michigan Medicine.
Phase:	2
Description of Sites/Facilities Enrolling Participants:	Study operations will be conducted at Michigan Medicine University Hospital and Cardiovascular Center; Ann Arbor, MI USA.
Description of Study Intervention:	This will be a three-arm parallel trial. Participants will be randomized to intravenous dextrose 5% in water (placebo), low-dose caffeine citrate (1.5 mg/kg), or high-dose caffeine citrate (3 mg/kg) at multiple postoperative time points over a 30-minute infusion period.
Study Duration:	The estimated trial duration will be approximately four years.
Participant Duration:	Total study duration for patients will be approximately 30 days.

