A recent single-center clinical trial was designed to test the effects of caffeine on early neurocognitive recovery after major laparoscopic surgery in adults.²⁰ Results demonstrated that caffeine significantly reduced the risk of PACU delirium (Fig. 2). However, PACU delirium was a post-hoc, exploratory outcome, with a low fragility index³¹ between placebo and caffeine groups. Nonetheless, patients randomized to caffeine also demonstrated increased neurophysiologic signs of arousal based on EEG analysis in the PACU.²⁰ A secondary analysis of the EEG data demonstrated increased neurophysiologic *criticality*, which reflects a point of dynamic instability that may allow for flexible access to a wide range of brain states (and thus, improved cognitive function).²¹ Lastly, in this trial, caffeine was not found to reduce opioid consumption, subjective pain reporting, or anesthetic emergence time. However, the small sample size (n=65) precludes firm conclusions. Of note, no major adverse events were reported in relation to caffeine, and early postoperative hemodynamic recovery patterns were similar compared to placebo.

[figure not shown]

Fig. 2. PACU delirium was significantly reduced in patients receiving intravenous caffeine (4/33, 12%) compared to placebo (10/30, 33%; $p=0.04$) during surgical closure.

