3 OBJECTIVES AND ENDPOINTS

OBJECTIVES	ENDPOINTS	JUSTIFICATION FOR ENDPOINTS
Primary		
To determine whether intravenous caffeine reduces the incidence of postoperative delirium	--The primary endpoint is delirium, as measured via long-form Confusion Assessment Method (CAM), obtained one hour after PACU admission and twice daily for the first three postoperative days. The CAM will be complemented by a validated chart review method ^{65,66} to mitigate missing delirium assessments.	The CAM is the most widely used measure for identification of delirium worldwide, validated in >22 studies with sensitivity and specificity of >90%. ^{1,67,68}
Secondary		
To determine whether caffeine reduces delirium severity	-- A secondary endpoint will be delirium severity, as measured via the same long-form CAM (CAM-S score).	CAM-S is a continuous scoring metric based on the long-form CAM (scored 0-19, 19 = highest severity). The CAM-S demonstrates high inter-rater reliability (0.88 – 0.92) and strong correlation with important clinical outcomes, including hospital length of stay, cognitive and functional decline, discharge disposition, and mortality. ²
To determine whether caffeine reduces delirium duration	-- An additional secondary endpoint related to delirium will be delirium duration, as measured by the cumulative number of days (n) with a positive delirium screen.	Delirium duration is associated with poor hospital outcomes. ⁶⁹

The Caffeine, Postoperative Delirium, And CHange IN Outcomes after Surgery-2 (CAPACHINOS-2) Study Protocol <2.0>

Version <2.0>
<14 December 2022>

OBJECTIVES	ENDPOINTS	JUSTIFICATION FOR ENDPOINTS
To determine whether intraoperative caffeine improves patient-reported quality of recovery	-- Patient-reported 15-item Quality of Recovery score, ³ which will be assessed in the afternoon on postoperative day two.	The original Quality of Recovery ³³ scale has been used for 20 years in perioperative clinical trials research. Extensive validity, ⁷⁰ reliability, ⁷⁰ and minimal clinically important difference data ³⁵ have been published. This scale was also recently endorsed by the Standardized Endpoints in Perioperative Medicine Initiative. ⁷¹ Caffeine is postulated to ameliorate pain and postoperative confusion, which are each independently associated with poor recovery on this scale. ³⁴

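### The primary endpoint is delirium incidence, but the GEE specified for it does not fix the unit of analysis and, on its likelier reading, tests average delirium prevalence instead

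*Protocol*

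**What the plan says.** The hypothesis in Section 9.1 is that caffeine "will reduce the incidence of postoperative delirium as identified by the long-form CAM screening tool". The synopsis also gives the primary endpoint as a percentage incidence, and the planning rates in Section 9.2 are incidences (placebo 30%, low dose 10–30%, high dose 10–15%). Section 3 schedules the CAM to be "obtained one hour after PACU admission and twice daily for the first three postoperative days", which is seven assessments. Sections 3 and 9.1 add chart review to the in-person CAM.

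For the test, Section 9.4.2 says "The primary analytical test will be a multivariable logistic regression model that will follow the GEE approach". It names no unit of analysis, no time term and no rule for collapsing the assessments. Section 9.4.3 adds "All GEE models will use the empirical parameter estimates with an exchangeable correlation matrix". The sentence before that one begins with non-repeated continuous measures and continues "and binary outcomes (e.g., postoperative delirium, headache), we will use the same GEE modeling approach".

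Section 9.2 sizes the trial by "GEE Tests for Multiple Proportions in a Cluster-Randomized Design" without giving a cluster size or an intracluster correlation. The title of its method reference (reference 90) concerns time-averaged comparison of repeated binary outcomes.

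**The concern.** Incidence counts each patient once. A logistic GEE over repeated CAMs counts each assessment, so a patient positive on six CAMs contributes six times as many positive results as a patient positive on one. Its arm coefficient compares the average odds that an assessment is positive, which mixes how many patients become delirious with how long they stay so. Duration is already a separate secondary endpoint.

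The two tests have different nulls. A trial analysed by the repeated-CAM model could report lower incidence when only episode length had changed, or miss a real fall in incidence. The second risk bears on this trial because its supporting delirium evidence is for the PACU: "Results demonstrated that caffeine significantly reduced the risk of PACU delirium" (Section 2.2). An episode confined to the PACU is one positive CAM out of seven.

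**Working it through.** **Inputs from the protocol.** Seven CAMs (1 + 2 × 3, Section 3). N = 250, about 10% dropout, α = 0.05 (Section 9.2), 1:1:1 allocation (Section 4.1), two-sided tests (Section 9.4.1). This gives 250/3 ≈ 83 randomised and 225/3 = 75 evaluable per arm. **Assumed, because the protocol gives no figure:** positive CAMs per episode, complete assessments, no covariates.

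**The plan's own figure (80–95% power).** The check used one record per patient, 75 per arm and a 2-df test of the three arms. Each range covers pooled, unpooled and logit variances, and rates are placebo/low/high.

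| Rates | Power |
|---|---|
| 30/10/10% | 87.7–93.5% |
| 30/30/10% | 82.1–94.9% |
| 30/10/15% | 81.7–84.8% |
| 30/30/15% | 56.7–67.2% |
| 30/20/15% | 50.5–51.7% |

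The stated range is met at the first three combinations but not at the last two. With M repeats the variance is multiplied by (1 + (M−1)ρ)/M. For M = 7 and an assumed ρ = 0.5 the factor is 4/7. Then 30/30/15% reaches 82% (logit variance), or 81% with ρ = 0.7 (unpooled variance), but 30/20/15% stays at 76% and 64%. This hints that repeats were counted in the sizing. It does not prove it, because M and ρ are not given.

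**What each test measures.** Let θ be incidence, L the positive CAMs in a delirious patient, and K the positive CAMs per patient (0 if never delirious).

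- Average prevalence: p = θ·E[L]/7.
- Balanced logistic GEE: effect = logit(p₀) − logit(p₁). Robust SE per arm = √(Var(K)/(49n)) / (p(1−p)), with Var(K) = E[K²] − (E[K])².
- The per-patient test depends on θ alone.

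The nulls separate at once: 0.30 × 2/7 = 8.6% and 0.15 × 4/7 = 8.6%. Incidence is halved and prevalence is equal. In simulation at 75 per arm the GEE rejected in 4.5% of trials and the per-patient test in 61%.

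**One case in full.** Brief = 1 CAM; long = 2 to 6 equally likely (mean 4, mean square (4+9+16+25+36)/5 = 18). Placebo is 15% brief and 15% long; active is 7.5% and 7.5%.

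- Placebo: E[K] = 0.75, p = 0.107, Var(K) = 2.85 − 0.5625 = 2.2875, SE = 0.0249/0.0957 = 0.261.
- Active: E[K] = 0.375, p = 0.0536, Var(K) = 1.425 − 0.1406 = 1.2844, SE = 0.0187/0.0507 = 0.369.
- z = 0.751/0.452 = 1.66, so power = Φ(1.66 − 1.96) = 38%.

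The same formula for the other cases, beside the simulations:

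| Case (placebo → active) | p | Effect / SE | GEE, formula, n = 75 | GEE, simulated | Per patient, simulated |
|---|---|---|---|---|---|
| 30→15%, brief/long 15/15 → 7.5/7.5 | 10.7 → 5.4% | 0.751/0.452 | 38% | 43–44% (n = 83) | 65–66% |
| 30→15%, lengths 1–3 in both arms | 8.6 → 4.3% | 0.739/0.380 | 49% | 51% (n = 75, mean length 2) | 62% |
| 30→15%, only brief prevented, 15/15 → 0/15 | 10.7 → 8.6% | 0.247/0.414 | 9% | 7.5–10% | 60–65% |
| 30% in both, brief/long 10/20 → 20/10 | 12.9 → 8.6% | 0.453/0.368 | 23% | 27% (n = 83) | 5–6% |
| 30% in both, lengths 2–6 → 1–3 | 17.1 → 8.6% | 0.792/0.315 | 71% | 75% (n = 83) | 5–6% |

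**Per-patient check, 30% vs 15%, n = 75.** (0.15 − 1.96·√(2·0.225·0.775/75)) / √((0.21 + 0.1275)/75) = (0.15 − 0.1337)/0.0671 = 0.24, so power is 59.6%.

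**Two limits.** With identical arms both tests reject in about 5%. If every episode lasted exactly two CAMs, Var(K) = 4θ(1−θ) and z = 0.739/0.346 = 2.14, so GEE power would be about 57%. The loss at an unchanged mix therefore comes from the spread in episode length.

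**The case against.** The strongest reply is that repeated CAMs as the response are inferred, not stated. The exchangeable matrix is given under secondary endpoints, and the preceding sentence applies the same GEE to non-repeated measures and names postoperative delirium among binary outcomes. The matrix alone therefore does not prove several rows per patient. Section 9.2 names a software module but no cluster unit, and its rates are incidences. This stands, and it is why the point is conditional. It does not settle the matter the other way. Headache is in the same list and is assessed at every delirium timepoint (Section 8.1). Allocation is by individual at one centre, so the patient is the only evident cluster, and the sizing reference is about time-averaged responses.

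A reader might infer that the primary test is certainly the wrong one, or that it gives false positives for an inert drug. The documents support neither. With one record per patient the model is valid for incidence, and with identical arms both tests hold their level. The high rejection rates at equal incidence arise only if caffeine truly shortens delirium, so the fault would be in what the result is called.

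The largest power losses also rest on assumptions. They need brief episodes to be selectively prevented or the remaining ones to lengthen. The PACU result came from one infusion at closure, whereas this trial also doses on two postoperative mornings. A day-level response would give about four rows rather than seven.

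Deriving the response is often left to an SAP. Here, however, the protocol itself fixes the model, the matrix and the sizing method, and these pull away from its own hypothesis.

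**Conclusion.** The point holds in conditional form. The hypothesis and planning rates are per-patient incidence, while the stated tools are those of a repeated-measures analysis, and Section 9.4.2 does not say which applies. On the likelier reading the primary coefficient tests prevalence. On the other reading the test is sound, but the sizing method does not belong to it. On neither reading do all the stated elements fit together.

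The most neutral measure of size is the case with an unchanged mix of episode lengths: about 40–51% power against about 60–66% per patient for 30% vs 15%. The 8–10% power and the 25–75% rejection at equal incidence show how far the two nulls can part. They are not forecasts. All figures assume seven complete CAMs, 75–83 per arm, no covariates and episode lengths that the protocol does not supply.

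**What to change.** In Section 9.4.2, define the primary response as one binary value per patient: delirium at any time from the PACU assessment through the POD3 afternoon, by CAM or by the chart review already specified in Sections 3 and 9.1. Analyse it by logistic regression with the two dose contrasts against placebo and the covariates already listed. State how patients with incomplete assessments are classified, since fewer assessments mean fewer chances to be positive. In Section 9.4.3, exempt this endpoint from the exchangeable-matrix sentence. Keep the repeated-CAM GEE as a secondary analysis labelled as the effect on average prevalence. Section 9.2 should then name a sizing method for one value per patient.

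This changes wording only and needs no new data or patients. The downside is less power if caffeine mainly shortens episodes, an effect that the duration endpoint and the secondary GEE still cover.
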